Preliminary clinical data suggest that restoration of the GH axis in obesity is a potential therapeutic strategy in NAFLD. Our group demonstrated that once daily GH administration by subcutaneous injection with an increase in IGF-1 levels to the upper-normal range reduced IHL by 1H-MRS in overweight/obese individuals unselected for NAFLD.[29] Of importance, only a subset of study subjects would have qualified as having NAFLD. Despite this, we detected a decrease in IHL. These pilot data are exciting with regard to the potential for GH augmentation as an effective therapeutic strategy in NAFLD. **However, studies demonstrate that GH pulsatility may be particularly important for effective lipolysis,[43] and that a more continuous (versus pulsatile) administration of GH may downregulate GH signaling pathways.[44]** Thus importantly, in contrast to once daily GH administration, restoration of endogenous GH pulsatility via a GH secretagogue like ibutamoren may enhance the lipolytic effects of GH[43, 44] while preserving endogenous feedback loops, enhancing both efficacy and safety profiles.

A6. SCIENTIFIC PREMISE AND HYPOTHESIS:

The proposed intervention, ibutamoren, is an orally administered, long-acting ghrelin mimetic that has direct immune effects that target specific areas of known immune dysregulation in NAFLD/NASH, physiologically restores endogenous GH pulse amplitude, and has a strong safety profile with prior administration in over 1,200 individuals (adults and children).[45-53] **Our overarching hypothesis is that oral ibutamoren administration will improve steatosis, inflammation and fibrosis in subjects with overweight/obesity and NASH.**

2. Specific Aims and Objectives

A. SPECIFIC AIM 1: We hypothesize that GH augmentation by oral ibutamoren for 6 months in subjects NAFLD compared to an historically studied placebo group subjects for 6 months will:

Aim 1A: Decrease hepatic steatosis, as measured by 1H-MRS (**primary endpoint**)

Aim 1B: Decrease hepatic inflammation and fibrosis, as measured by
[REDACTED] (**primary endpoint**)

3. General Description of Study Design

[figure not shown]
Overview of Study Design (Figure 1, Table 1)

An overview of the study design is provided in Figure 1. Aim 1 examines the effect of Ibutamoren mesylate administration on intrahepatic lipid accumulation in 10 men and women with NAFLD and relative IGF-1 deficiency.

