A high-contrast, black and white image showing a series of horizontal white bars of varying lengths on a black background. The bars are positioned on the left side of the frame, with a larger cluster in the center and smaller ones towards the top and bottom edges. The image has a grainy, high-contrast texture, resembling a film scan or a digital noise pattern.

5. Subject Enrollment

[figure not shown]
A. Enrollment

Subjects responding to the initial recruitment advertisements will undergo initial prescreening by phone, and if potentially eligible for participation, will be invited to participate in screening visits to determine study eligibility. For **Specific Aim 1 (main study)**, we expect to screen 50 radiographically-proven NAFLD subjects and enroll 12 NAFLD subjects, 6 women and 6 men, with NAFLD, in order to obtain 10 completers.

B. Consent

All subjects will receive the written consent form or virtual eConsent form via MGB-approved eConsent platform (REDCap) for the study as well as the Human Subject's Bill of Rights. These documents will be read by the study subjects and also reviewed by the study subject with a

clinician or licensed nurse practitioner prior to participating in the study. Any questions, concerns, or ambiguities will be clarified by a licensed physician investigator or licensed nurse practitioner prior to the patient signing consent. Potential study subjects will sign informed consent and only then will begin participation in the study. If new information is ascertained during the study, we will modify our consent and re-consent our patients.

C. Study Drug Start

Aim 1 participants who qualify and are enrolled in this study will start the medication after baseline testing is complete (as described below). This is an open-label pilot study.

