6. STUDY PROCEDURES

Table 1. Aim 1 Schedule of Procedures

Open label ibutamoren mesylate (oral 25 mg daily) will be administered to 12 subjects (goal 10 completers) with comparison to identically-studied, historical placebo-group controls.

Visit Components	Screen	Baseline	1 month	2 month lab check	3 month	4.5 lab check	6 month
COVID-19 Screening Phone Call	x	x	x	x	x	x	x
Liver Ultrasound	x						
NAFLD Fibrosis Score		x					x
DXA		x					x
MRI/MRS		x					x
Waist-Hip Ratio		x					x
Endocrine/Misc. Labs							
Blood: TSH	x						
Blood: HCV Antibody	x						
Blood: HBV Surface AG	x						
Peripheral Blood Mononuclear Cells (PBMCs)		x					x
Ibutamoren Stimulation Test		x					
Blood: Insulin, lipids		x					x
Safety Evaluation							
Physical Exam***	x	x	x		x		x
Blood: INR	x						
Blood: Creatinine	x						
Blood: CBC	x						x
Blood: Liver function tests	x	x	x	x	x	x	x
Blood: Fasting Glucose	x	x	x		x		x
Blood: HbA1c	x				x		x
Blood: IGF-1	x		x		x		x
Urine pregnancy test	x	x	x		x		x

*** Optional, limited physical exam will be performed at the discretion of the study provider

A. Study Visits for Specific Aim 1:

1. Screening Visit : (n=50, approximately 50% women)

After informed consent, subjects will be evaluated for eligibility with:

- A basic metabolic panel, INR, CBC, TSH, fasting glucose, hemoglobin A1c (HbA1c), hepatic function panel, and IGF-1 will be performed.
- Records of cancer screenings appropriate for the age and gender of the participant will also be requested.
- Height and weight will be measured, and BMI will be calculated.
- A history and physical will be performed.
- A pregnancy test will be performed in all premenopausal women with childbearing potential.
- A liver US or liver ultrasound elastography [REDACTED] will be performed in study subjects who do not have a known diagnosis of NAFLD.
 - Due to limited ultrasound sensitivity for screening for fatty liver, subjects will be invited to a screening MRI for assessment of NAFLD if the subject otherwise qualifies for the study but has a negative screen ultrasound for NAFLD.
- Individuals will be queried regarding alcohol use as well as for history of other chronic liver disease.
- Hepatitis C antibody and Hepatitis B surface antigen tests will be performed in study subjects who have not had this as a part of their clinical care.
- Serum and plasma samples will be drawn and stored frozen for future testing.

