Remote Blood Draws for Screening [REDACTED]: to allow maximum flexibility with our subject's schedules, the blood tests listed above can be drawn at [REDACTED] facility close to the subject's home location. Screen aliquots will not be obtained during a remote blood draw.

2. Baseline and 6-month visit: (n=15 at baseline, n=10 completers: approximately 50% women)

The baseline visit will occur within 12 weeks after the screening visit. The following assessments will be made during the baseline visit, which will occur within a 30-day period and can occur in one session or over multiple days depending on schedules and patient preference. The 6-month visit will be performed during a +/- 3 week interval around the indicated return time to allow for potential scheduling conflicts. The order of the tests may vary depending on the subject and TCRC availability.

- Interview to determine whether any changes in medical history since the screening visit has occurred
- BMI, waist-hip-ratio measured
- In the fasting state, a blood sample will be obtained to determine glucose, insulin, GH, IGF-1 (6 mo only), CBC (6 mo only), HbA1c (6 mo only), lipids, triglycerides, and liver function tests. Note: Pre-treatment HbA1c, IGF-1, CBC will have already been performed at the screening visit and are not repeated at baseline.
- Fasting glucose will be performed at baseline and 6-month visits. Aliquots for insulin measurements will be taken at these time points as well.
- A fasting GH-stimulation test will be performed at the baseline visit only using ibutamoren 25 mg oral dose with GH levels measured at 0, 30, 60, and 90 and

120 minutes. All hormones will be measured using gold standard techniques (including IGF-1 by LC/MS).

- Serum and plasma samples will be drawn and stored frozen for future testing.
- [REDACTED]
- MRI: 1H-MRS of the right hepatic lobe will be performed at the baseline and 6-month visits to quantify hepatic lipid content and other fat depots. [REDACTED] sequences will also be performed for noninvasive analysis of hepatic iron content, inflammation and fibrosis. Sequences will also be performed to assess pancreatic fat, inflammation and fibrosis as well as renal inflammation and fibrosis. The entire protocol will be scheduled for one 45 minute MRI slot.
 - A baseline MRI will be acquired if the screen MRI occurred more than 6 weeks prior to baseline procedures. Otherwise, the MRI procedure at baseline is not required.

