- Dual-energy x-ray absorptiometry (DXA) scan will be performed at the baseline and 6-month visits to determine body composition.

3. Drug Start: Ibutamoren will be started at a dose of 25 mg orally daily, starting after baseline procedures are complete. All subjects receive drug in this open label study.

4. 1-month follow up visit: (n=15, approximately 50% women): These visits will be performed between 3-6 weeks to allow for potential scheduling conflicts.

- Study subjects will be assessed for interim medical history and side effects to study drug. An optional physical exam will be performed as indicated per the discretion of the study clinician.
- IGF-1 will be measured as a safety lab
- Pregnancy tests will be checked for all premenopausal women [REDACTED]
- Fasting glucose and liver function tests will be measured as safety labs
- If the visit is on-campus (MGH), serum and plasma samples will be drawn and stored frozen for future testing.

5. 2-month lab draw: If 1 month transaminases (ALT or AST) are above the normal range and elevated compared to the baseline values, a 2-month (+/- 2 week interval) liver function panel will be measured. This blood draw can be performed remotely at [REDACTED] location or at MGH at the preference of the subject.

6. 3-month follow-up visit: (n=15, approximately 50% women)

These visits will be performed during a +/- 2 week interval around the indicated return time to allow for potential scheduling conflicts.

- Study subjects will be assessed for interim medical history and side effects to study drug. An optional physical exam will be performed as indicated per the discretion of the study clinician.
- IGF-1 will be measured as a safety lab at all follow-up visits
- Pregnancy tests will be checked for all premenopausal women
- Fasting glucose, HbA1c and liver function tests will be measured as safety labs
- If the visit is on-campus (MGH), serum and plasma samples will be drawn and stored frozen for future testing.

Either the 1-month or 3-month visit may be performed remotely per the discretion of the

study investigator; at least one of these visits will be performed in person.

7. 4.5-month lab draw:

A 4.5-month (+/- 2 week interval) fasting glucose and liver function tests will be measured as safety labs.

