General Considerations: IV placement and blood sampling is performed in the study, and there is a minor risk of infection, bruising, or syncope during a blood draw. There is also potential discomfort of having an IV placed and having blood drawn. Lightheadedness is a possible side effect from overnight fasting. The blood draws will be performed by trained staff who have certificates documenting their ability to draw blood.

B. Protection Against Risk

In addition to the formal safety monitoring plan described, below, the procedures to protect against or minimize potential risks include the following: (1) the assignment of unique study subject numbers to patients, (2) the use of these primary identifiers throughout the study, (3) storage of information in locked file cabinets, and (4) access limited to study personnel for these file cabinets and data. The blood draws will be performed by trained staff who are certified to draw blood. We are performing a physical examination and routine laboratory tests prior to allowing anyone to enter the protocol to ensure that subjects are medically stable. Close monitoring of patients throughout the study will ensure that adverse effects from our

interventions. All study subjects will be instructed on how to contact study clinicians in the case of an emergency.

8. Benefits

There is no expected benefit to participation in this study. If a subject receives ibutamoren in this protocol, it is possible that their amount of liver fat may decrease during the study. However, those effects are not promised or guaranteed. If benefits occur, there is no way to know how long they will last. If a medical condition is discovered, one will be referred to your physician. It is possible that information learned from this study may help improve therapy for people who are obese.

9. Statistical Analysis

A. Statistical power and Analysis

[figure not shown]
Aim 1A Statistical Power: The primary endpoint of Aim 1A is change in liver fat by 1H-MRS. With N=20 completers (10 open-label ibutamoren and 10 historical placebo-group controls studied with identical procedures from Protocol [REDACTED]

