[REDACTED] we will have 80% power to detect a 2% absolute difference in change in liver fat between GH and placebo utilizing an estimated SD of the change in liver fat of 1.6% based on a study of a diet-based intervention for NAFLD.[65] Notably, this calculation already allows for a generous dropout rate of 17% (2 dropouts from 12 enrolled). Additionally, Stanley *et al.*[66] reported a 2.9% change between a subcutaneous GH secretagogue and placebo, which is likely an underestimation of our expected effect given that study involved subjects unselected for NAFLD.

Aim 1B Statistical Power: The primary endpoint is the cT₁ Score by [REDACTED] We will have 80% power for a cohort of N=20 subjects with a two-tailed significance level of 0.05 to detect a difference of 76 ms in cT₁ between the ibutamoren and placebo groups assuming a SD of 57.4 ms as reported in a NAFLD treatment-study by Harrison *et al.*[67] Allowing for dropouts (n=18), the detectable difference in cT₁ is 80 ms. [REDACTED]

Aim 1A and 1B Data Analysis Plan: A pooled random slopes model analysis of treatment effect across sexes with weights equaling the frequency of sexes in the sample. A secondary analysis will test for the treatment-sex interaction. For all analyses, an intent-to-treat analysis will be performed. We will apply guidelines developed by the National Research Council regarding missing data.⁶⁶ Our primary analysis assumes that data is missing at random. We will conduct two sensitivity analyses: (1) assumes that the missing data is a function of the unobserved random effect⁸² and (2) tests the model's assumptions under other missingness mechanisms.⁸³

[REDACTED]

[REDACTED]

[REDACTED]

10. Monitoring and Quality Assurance

A number of procedures will be instituted to protect against potential risk involved in this prospective protocol, as follows:

[figure not shown]

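### The comparison with historical controls is adjusted only for sex in the readable text; a baseline-adjusted estimate should be prespecified beside the difference in change

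*Combined protocol and SAP*

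**What the plan says.** **Design.** Section 2 states both primary hypotheses as ibutamoren "compared to an historically studied placebo group subjects for 6 months". The text above Table 1 in Section 6 describes open-label treatment "with comparison to identically-studied, historical placebo-group controls", and Section 6 (Drug Start) adds "All subjects receive drug in this open label study". Section 5 discloses that "This is an open-label pilot study". Section 3 draws the controls from an earlier protocol whose identifier is redacted. Section 9 plans on ten per group: "With N=20 completers (10 open-label ibutamoren and 10 historical placebo-group controls studied with identical procedures".

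**Analysis.** The Section 9 analysis paragraph for Aims 1A and 1B specifies "A pooled random slopes model analysis of treatment effect across sexes with weights equaling the frequency of sexes in the sample". It adds a secondary treatment-by-sex test, intent-to-treat, a missing-at-random assumption and two missing-data sensitivity analyses. It states no baseline term, no covariate other than sex and no time coding. The paragraph itself has no redaction mark, but redacted blocks follow it.

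**Scans.** MRI/MRS is scheduled at baseline and 6 months only. Section 6 also says "subjects will be invited to a screening MRI for assessment of NAFLD if the subject otherwise qualifies for the study", which applies to people whose screening ultrasound was negative. It continues: "A baseline MRI will be acquired if the screen MRI occurred more than 6 weeks prior to baseline procedures". A more recent screening scan can therefore serve as the baseline scan.

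**Eligibility.** Section 7 lists unstable weight before entry among the exclusions, and says the criteria are meant to avoid confounding by, among other things, active weight loss. The numbered list in Section 4 has no such item.

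**The concern.** In a randomised trial, the difference in change and the baseline-adjusted difference estimate the same effect. Between non-randomised cohorts they need not. With ten per group and no matching or adjustment in the readable text, a baseline difference in liver fat or cT1 could pass into the reported treatment effect.

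The documents give one reason why change might depend on baseline. In some ibutamoren subjects the scan that established NAFLD may also be the baseline scan, which invites regression to the mean.

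The model's name does not settle the matter. Two scans per person cannot identify a random intercept, a random slope and a residual variance without a restriction. With complete data, a free group term at baseline reproduces the difference in mean change, and a shared baseline mean reproduces ANCOVA. If only one estimate is reported, readers cannot see how far the conclusion depends on that choice.

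Unstable weight is relevant for a related reason: weight change plausibly moves liver fat, so both cohorts should be screened for it in the same way or not at all.

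**Working it through.** **1. The plan's own figures.** Inputs from Section 9: 10 v 10, difference in change 2 points, SD of change 1.6. Two-sided 0.05 is stated for Aim 1B and assumed here for Aim 1A.
- Aim 1A: standard error = 1.6 × √(2/10) = 0.716, and 2/0.716 = 2.795. The normal approximation gives Φ(2.795 − 1.96) = 79.8%, which reproduces the stated 80%. The two-sample t test (18 df) gives 75.3%.
- Aim 1B: 76/(57.4 × √(2/10)) = 2.96. The t test gives 79.9%, which reproduces the stated 80%.

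Both are unadjusted two-group calculations.

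**2. Gap between the two analyses.** Difference = slope × baseline gap. Assumed values, not in the documents: gap 4 points, slope 0.2, baseline SD 6. Then 0.2 × 4 = 0.8 points, and 0.8/2 = 40% of the target.

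**3. Type I error with the SD of change held at 1.6.** Residual SD = √(1.6² − (0.2 × 6)²) = √1.12 = 1.06.
- *One common line, no drug effect.* The change score is biased by 0.8. Noncentrality = 0.8/0.716 = 1.118, and with 18 df it rejects 18.5% of the time. ANCOVA holds about 5%.
- *Each cohort regresses to its own mean, no drug effect.* The change score holds 5%. ANCOVA is biased by 0.8 and rejects about 31% of the time (31.0% and 31.7% in two runs of 40,000 simulated trials).

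Range over gaps of 2 to 6 and slopes of 0.1 to 0.2:

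| Scenario | Biased analysis | Type I error |
|---|---|---|
| Common line | Change score | 6% to 36% |
| Own mean | ANCOVA | 6% to about 54% |

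A slope of 0.3 is impossible on this SD, because 0.3 × 6 = 1.8 exceeds 1.6.

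**4. Second parameterisation.** Assume equal variances at both visits and a baseline to 6-month correlation r of 0.5 to 0.9. Baseline SD = 1.6/√(2(1 − r)), and the shift is (1 − r) × imbalance. If the baseline-adjusted effect is truly null:

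| Imbalance | Shift (points) | Share of target | Change-score type I error |
|---|---|---|---|
| 0.5 SD | 0.18 to 0.40 | 9% to 20% | 5.6% to 8.3% |
| 1 SD | 0.36 to 0.80 | 18% to 40% | 7.6% to 18.5% |

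**5. cT1, common line.** Treat 57.4 ms as an SD of change, which Section 9 does not say it is. Assumed gaps of 50 to 100 ms and slopes of 0.1 to 0.3 give a shift of 5 to 30 ms (7% to 39% of 76 ms) and change-score type I error of 5% to 20%. These are large gaps, 50/57.4 = 0.9 to 100/57.4 = 1.7 times the only cT1 SD given.

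**6. Power of the adjusted analysis.** With balanced baselines and the assumptions of step 4, the ANCOVA residual SD is 1.6 × √((1 + r)/2). Aim 1A power on 17 df is then 86% at r = 0.5 and 77% at r = 0.9, against 75.3% unadjusted.

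**The case against.** **The estimand is already clear.** The liver-fat endpoint is 6-month change, Aim 1A is powered on a difference in change, and a random slopes model would usually take the baseline scan as its time-0 response. This stands: the difference in change is the natural reading, and nothing suggests a shared baseline mean. What is left is that this reading carries no baseline adjustment.

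**Redaction may hide the rule.** A reader might infer that the contrast is open altogether, or that controls could be picked after their results are known. The documents do not support that. Redactions in Sections 3 and 9 fall where a selection rule could sit. The source is an earlier protocol, and if all its placebo participants are used there is nothing to select. The most that can be said is that the rule is not fixed in the readable text. The stated identity of procedures could even extend to screening, though the text does not say so.

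**ANCOVA is not uniformly safer.** Correct. At the same gap and slope its error in its bad case is larger than the change score's in its own (31% against 18.5%). A reader might infer that the unadjusted analysis is wrong and must be replaced; the figures do not show that.

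**The sizes are assumed.** Also correct. A gap of 2 with slope 0.1 raises the error only to about 6%. A reader might also use 1.6 as a residual SD and find much lower power, but Section 9 calls it the SD of the change, so 75.3% is the relevant t-test figure.

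**It is a disclosed pilot, and few subjects may take the screening-MRI route.** Both points limit the severity. Neither removes the value of showing both estimates. On weight, the investigator-discretion item in Section 4 could be used to exclude unstable subjects, but it is not the criterion that Section 7 names.

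**Conclusion.** The concern holds in a limited form. The use of historical controls is disclosed and is not itself an error, and the power figures reproduce. The weakness is that the readable plan offers one non-randomised contrast for each primary endpoint, adjusted for nothing but sex.

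Under the assumed gap of 4, slope of 0.2 and baseline SD of 6, the choice of analysis moves the liver-fat estimate by about 0.8 points, 40% of the target. Type I error is 18.5% for the change score if one line fits both cohorts, and about 31% for ANCOVA if each regresses to its own mean. No gap or slope is given in the documents, so these figures show sensitivity only and do not predict bias in this trial. Neither analysis removes drift or unmeasured differences between the studies.

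The mismatch on unstable weight between Sections 4 and 7 is a separate, direct inconsistency that rests on no assumption.

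**What to change.** 1. For liver fat and cT1, prespecify both the difference in 6-month change and an estimate adjusted for the endpoint's baseline value and sex. Name one as primary before 6-month data are analysed. Report both with confidence intervals, beside a table of baseline characteristics by group. State that neither removes drift or unmeasured differences between the studies.
2. Reconcile the weight-instability exclusion in Section 7 with the Section 4 list, and apply the result to both groups.
3. Minor, unless redacted text already covers it: confirm that the controls are all placebo participants of the earlier protocol who meet this trial's criteria on baseline data.

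**Cost.** Wording only; no new patients, visits or scans. Adjustment uses one degree of freedom (17 instead of 18) and loses some precision if baselines differ. With a gap of 4 and baseline SD 6, the within-group sum of squares is about 18 × 36 = 648, so the standard error grows by √((0.2 + 16/648)/0.2) = 1.06, about 6%. Item 3 could rule out some controls: with SD 1.6 and a 2-point difference, change-score power is 66% at 10 v 7 and 62% at 10 v 6, against 75.3% at 10 v 10.
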